Cover Page

Protocol including Statistical Analysis Plan

Last Approved Version & Date: Amendment 2, 11-Dec-2015

Protocol Title:

**A phase 2 multi-center investigation of efficacy of
ABI-009 (*nab*-rapamycin) in patients with
advanced malignant perivascular epithelioid cell tumors
(PEComa)**

A phase 2 multi-center investigation of efficacy of ABI-009 (*nab*-rapamycin) in patients with advanced malignant perivascular epithelioid cell tumors (PEComa)

INVESTIGATIONAL PRODUCT (IP):	ABI-009
PROTOCOL NUMBER:	PEC-001
Version History:	
Date Final:	June 16, 2015
Amendment 1	Aug 9, 2015
Amendment 2	Dec 11, 2015
IND NUMBER:	125,669
SPONSOR NAME/ ADDRESS:	AADI, LLC [name]

CONFIDENTIAL

This protocol is provided to you as an Investigator, potential Investigator, or consultant for review by you, your staff, and ethics committee/institutional review board. The information contained in this document is regarded as confidential and, except to the extent necessary to obtain informed consent, may not be disclosed to another party unless such disclosure is required by law or regulations. Persons to whom the information is disclosed must be informed that the information is confidential and may not be further disclosed by them.

PROTOCOL SYNOPSIS

Study Title

A phase 2 multi-center investigation of efficacy of ABI-009 (*nab*-rapamycin) in patients with advanced malignant perivascular epithelioid cell tumor (PEComa)

Study Number: PEC-001

Study Phase: 2

Name of Investigational Product (IP)

ABI-009, rapamycin protein-bound nanoparticles for injectable suspension (albumin bound), *nab*-rapamycin, nanoparticle albumin-bound rapamycin

Indication

Patients with advanced (metastatic or locally advanced) malignant PEComa, who have not been previously treated with an mTOR inhibitor.

Objectives

Primary Objective

The primary objective of this study is to investigate the efficacy of the mTOR inhibitor ABI-009 in advanced malignant PEComa.

Secondary Objectives

The secondary objectives are to further investigate the efficacy and safety of intravenous (IV) ABI-009 100 mg/m² given weekly for 2 of 3 weeks in patients with advanced malignant PEComa.

Exploratory Objectives

- To evaluate investigator assessed ORR
- To evaluate pharmacokinetic/pharmacodynamic relationships for safety and/or efficacy endpoints
- To evaluate tumor biomarkers

Endpoints

Primary Endpoint

The primary endpoint is objective overall response rate (ORR), as determined by independent radiologic assessment using Response Evaluation Criteria in Solid Tumors (RECIST) v1.1.

Secondary endpoints

The secondary endpoints are duration of response (DOR), progression-free survival (PFS) rate at 6 months, PFS, overall survival (OS), safety/tolerability.

- DOR, PFS at 6 months, median PFS, and median OS will be assessed separately in subgroups of patients with metastatic disease and locally advanced disease.
- Safety will be analyzed in all treated patients.

Exploratory Endpoints

- Investigator assessed ORR
- Pharmacokinetic/pharmacodynamic relationships for safety and/or efficacy endpoints
- To evaluate tumor biomarkers:
 - **Blood samples** will be obtained for cell-free plasma DNA collection (pretreatment, Cycle 4/Day 1, and post-treatment) for all patients.
 - Molecular analysis of cell-free plasma DNA assay using next-generation sequencing to assess the prevalence of mutations identified in the primary tumor sample over time as a measure of response to therapy.
 - **Tumor biopsy mutation analysis to assess resistance mechanisms.** Pre-treatment tumors (archival or fresh tissue biopsies) are required for all patients on this study to confirm diagnosis. This sample will also be used for baseline mutational analysis. In addition, an optional tumor biopsy will be collected for patients who provide additional consent at the end of treatment and/or if a patient experiences progression while on study.

Study Design

This study is a prospective phase 2, single arm, open-label, multi-institutional study to determine the efficacy and safety profile of ABI-009 administered by IV infusion in patients with advanced malignant PEComa.

The study will be conducted in compliance with International Conference on Harmonisation (ICH) Good Clinical Practices (GCPs).

Sample Size

At least 30 evaluable patients will be enrolled.

Study Population

Malignant PEComa histology may be assessed locally in each institution for enrollment but will be retrospectively confirmed by a centralized review for every patient after enrollment to meet prespecified criteria for malignant PEComa. If a patient does not meet retrospectively these criteria, a replacement will be considered.

Patient Eligibility

Inclusion Criteria

A patient will be eligible for inclusion in this study only if all of the following criteria are met:

1. Patients must have a histologically confirmed diagnosis of malignant PEComa that is either metastatic or locally advanced and for which surgery is not a recommended option.
2. Patients must have available tumor block along with the corresponding pathology report (or approximately 30 unstained slides, with a minimum of 16 slides), and/or fresh biopsy to allow retrospective centralized confirmation of malignant PEComa and for mTOR pathway analysis and biomarker analysis.
3. Patients must have one or more measurable target lesions by CT scan or MRI. Measurable disease by RECIST v1.1.
4. Patients must not have been previously treated with an mTOR inhibitor.
5. Prior treatment (investigational or other), chemotherapy, radiotherapy, surgery, or other therapeutic agents (except mTOR inhibitors) is allowed, if completed after 5 half-lives or ≥ 28 days prior to enrollment, whichever is shorter.
6. Eligible patients, 18 years or older, with Eastern Cooperative Oncology Group (ECOG) performance status 0 or 1.
7. Patients must have the following blood chemistry levels at screening (obtained ≤ 14 days prior to enrollment (local laboratory):
 - a. total bilirubin $\leq 1.5 \times$ upper limit of normal (ULN) mg/dl
 - b. AST $\leq 2.5 \times$ ULN ($\leq 5 \times$ ULN if attributable to liver metastases)
 - c. serum creatinine $\leq 1.5 \times$ ULN
8. Adequate biological parameters as demonstrated by the following blood counts at screening (obtained ≤ 14 days prior to enrollment, local laboratory):
 - a. Absolute neutrophil count (ANC) $\geq 1.5 \times 10^9/L$;
 - b. Platelet count $\geq 100,000/mm^3$ ($100 \times 10^9/L$);
 - c. Hemoglobin ≥ 9 g/dL.
9. Serum triglyceride < 300 mg/dL; serum cholesterol < 350 mg/dL.

10. Male or non-pregnant and non-breast feeding female:

- Females of child-bearing potential must agree to use effective contraception without interruption from 28 days prior to starting IP and while on study medication and have a negative serum pregnancy test (β -hCG) result at screening and agree to ongoing pregnancy testing during the course of the study, and after the end of study treatment. A second form of birth control is required even if she has had a tubal ligation.
- Male patients must practice abstinence or agree to use a condom during sexual contact with a pregnant female or a female of childbearing potential while participating in the study. A second form of birth control is required even if he has undergone a successful vasectomy.

11. Life expectancy of >3 months, as determined by the investigator.

12. Ability to understand and sign informed consent.

13. Willingness and ability to comply with scheduled visits, laboratory tests, and other study procedures.

Exclusion Criteria

A patient will not be eligible for inclusion in this study if any of the following criteria apply:

1. Patients with lymphangioleiomyomatosis (LAM) are excluded.
2. Known active uncontrolled or symptomatic central nervous system (CNS) metastases. A patient with controlled and asymptomatic CNS metastases may participate in this study. As such, the patient must have completed any prior treatment for CNS metastases ≥ 28 days (including radiotherapy and/or surgery) prior to start of treatment in this study and should not be receiving chronic corticosteroid therapy for the CNS metastases.
3. Active gastrointestinal bleeding.
4. Pre-existing thyroid abnormality is allowed provided thyroid function can be controlled with medication.
5. Uncontrolled serious medical or psychiatric illness. Patients with a “currently active” second malignancy other than non-melanoma skin cancers, carcinoma in situ of the cervix, resected incidental prostate cancer (staged pT2 with Gleason Score ≤ 6 and postoperative PSA <0.5 ng/mL), or other adequately treated carcinoma-in-situ are ineligible. Patients are not considered to have a “currently active” malignancy if they have completed therapy and are free of disease for ≥ 1 year).
6. Liver-directed therapy within 2 months of enrollment. Prior treatment with radiotherapy (including radio-labeled spheres and/or cyberknife, hepatic arterial embolization (with or without chemotherapy) or cyrotherapy/ablation) is allowed if these therapies did not affect the areas of measurable disease being used for this protocol.

7. Recent infection requiring systemic anti-infective treatment that was completed ≤ 14 days prior to enrollment (with the exception of uncomplicated urinary tract infection or upper respiratory tract infection).
8. Uncontrolled diabetes mellitus as defined by HbA1c $>8\%$ despite adequate therapy.
9. Unstable coronary artery disease or myocardial infarction during preceding 6 months.
10. Receiving any concomitant antitumor therapy.
11. Patients with history of interstitial lung disease and/or pneumonitis, or pulmonary hypertension.
12. Use of strong inhibitors and inducers of CYP3A4 within the 14 days prior to receiving the first dose of ABI-009. Additionally, use of any known CYP3A4 substrates with narrow therapeutic window (such as fentanyl, alfentanil, astemizole, cisapride, dihydroergotamine, pimozide, quinidine, terfanide) within the 14 days prior to receiving the first dose of ABI-009.
13. Known Human Immunodeficiency Virus (HIV).
14. Active Hepatitis B or Hepatitis C.

Length of Study

The study is expected to take approximately 32 months from first patient enrolled to last patient follow-up, including approximately 24 months of enrollment period, an estimated 6 months of treatment (or until treatment is no longer tolerated) and an end of treatment visit at 4 weeks (± 7 days) after last treatment.

The End of Study (EOS) defined as either the date of the last visit of the last patient to complete the study, or the date of receipt of the last data point from the last patient that is required for primary, secondary, and/or exploratory analysis, as pre-specified in the protocol.

End of Treatment (EOT) for a patient is defined as the date of the last dose of ABI-009. End of Treatment Visit for a patient is when safety assessments and procedures are performed after the last treatment, which must occur at least 4 weeks (± 7 days) after the last dose of ABI-009.

Follow-up period is the on-study time period after the EOT Visit. All patients that discontinue study drug and have not withdrawn full consent to participate in the study will continue in the follow-up phase for survival and initiation anticancer therapy. Follow up will continue approximately every 12 weeks (± 3 weeks), until death, withdrawal of consent, or the study closes, whichever is the earliest. This evaluation may be made by record review and/or telephone contact.

Study Treatments

Patients will receive ABI-009 100 mg/m² for 2 of every 3 weeks by IV infusion over 30 minutes. Two dose reduction levels will be allowed: 75 mg/m² and 56 mg/m². Patients will continue to therapy until disease progression, unacceptable toxicity, until in the opinion of the investigator the patient is no longer benefiting from therapy, or at the patients discretion.

Overview of Key Efficacy Assessments

Patients will be evaluated for complete response (CR), partial response (PR), stable disease (SD), or progressive disease (PD) by CT imaging. Contrast enhanced MRI can also be used, as long as the same modality is used throughout the study. Baseline scan results can be accepted from outside institutions, but must be done within 4 weeks of starting therapy and must include (as clinically indicated), chest abdominal, and pelvic CT or MRI. The first response assessment by CT or MRI scans documenting target lesions will be done 6 weeks after first treatment and should be repeated every 6 weeks for the first year, then every 12 weeks thereafter until disease progression. If an initial observation of objective response (CR or PR) is made, a confirmation scan should be done at 6 weeks after initial observation. Scans should continue on schedule regardless of delays in ABI-009 dosing. The primary endpoint, ORR, will be determined by independent radiologist(s). The independent radiologic review will follow a separate imaging charter.

After disease progression, patients will be followed for survival every 12 weeks, or more frequently as needed, until death, withdrawal of consent, or the study closes, whichever is the earliest.

Overview of Key Safety Assessments

Safety and tolerability will be monitored through continuous reporting of treatment-emergent and treatment-related adverse events (AEs), AEs of special interest, laboratory abnormalities, and incidence of patients experiencing dose modifications, dose delay/dose not given, dose interruptions, and/or premature discontinuation of IP due to an AE. All AEs will be recorded by the investigator from the time the patient signs informed consent until 28 days after the last dose of IP. Adverse events will be graded by National Cancer Institute (NCI) Common Terminology Criteria for Adverse Events (CTCAE) v4.03.

Physical examination, vital sign, laboratory assessments (eg, serum chemistry, hematology), and ECOG performance status will be monitored. All SAEs (regardless of relationship to IP) will be followed until resolution. Laboratory analysis will be performed as per study schedule.

Statistical Considerations

Efficacy Analyses:

The primary analysis will address all study objectives and it will be conducted when all patients have had the opportunity to be treated for at least 6 months. All primary, secondary, and exploratory efficacy and safety analyses will be conducted at the time

of the primary analysis, with the exception of the biomarkers which may be analyzed at a later date.

The primary endpoint is ORR by independent radiologic review, and is defined as the proportion of patients who achieve a confirmed PR or CR per RECIST 1.1.

The focus of the study is to estimate the ORR in patients treated with ABI-009. The number and percentage of patients achieving response will be summarized and an exact 95% confidence interval (CI) will be provided. Assuming an observed ORR of 30%, the lower bound of the 95% CI for the estimated ORR will exclude values less than 14.7%. With 30 patients the half-width of the 95% CI for the estimated ORR will be no more than 18.7%.

Analysis of secondary efficacy endpoints DOR, PFS rate at 6 months, PFS, and OS will be done separately for 2 subgroups of patients: 1) those with metastatic disease; and 2) those with locally advanced disease for which surgery is not a recommended option. Some of the patients in the locally advanced subgroup may be clinically indicated to receive surgery if there is sufficient tumor shrinkage, which would introduce a bias to the analysis.

For patients with metastatic disease, DOR, PFS at 6 months, median PFS, and OS will be summarized using Kaplan-Meier (KM) analysis. Quartiles with 95% CIs will be summarized. The number of patients with locally advanced disease for which surgery is not an option is expected to be small; therefore DOR, PFS at 6 months, median PFS, and OS for these patients will be summarized by descriptive statistics.

Safety Analyses:

The treated population (Full Analysis Set) will be the analysis population for all safety analyses. Adverse events will be coded using the Medical Dictionary for Medical Activities (MedDRA) and grouped by their system organ class and preferred term. Summary tables will include the number and percentage of patients with AEs, serious AEs, fatal AEs and other AEs of interest. Safety will be analyzed in both patient groups together (metastatic and locally advanced).

An external Data Monitoring Committee (DMC) will assess safety data approximately when a third of patients enrolled and received at least 2 cycles of therapy. For a full description of statistical analysis methods please refer to [Section 10](#).

TABLE OF CONTENTS

TITLE PAGE	1
PROTOCOL SYNOPSIS.....	5
LIST OF ABBREVIATIONS AND DEFINITIONS OF TERMS	17
1. INTRODUCTION.....	21
1.1. Malignant PEComa Disease Background	21
1.2. ABI-009 Background	23

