1.2.2.3. ABI-009 (nab-Rapamycin) Pharmacokinetics (PK)

ABI-009 produced a fairly dose proportional increase of C_{max} and AUC across the dose range tested, and it significantly inhibited mTOR targets S6K and 4EBP1.

ABI-009 has unique characteristics amongst the available mTOR inhibitors. The PK profile of rapamycin administered as ABI-009 is categorically different from those of the other oral or IV administered mTOR inhibitors. Intravenous infusion of ABI-009 results in high C_{max} of rapamycin upon administration followed by a long half-life of approximately 60 hrs that allows once weekly dosing. Peak levels of rapamycin after ABI-009 are well above 1000 ng/mL range that may have significant tumor penetration effect. Oral mTOR inhibitors such as rapamycin or everolimus have poor absorption with a high inter- and intra-patient variability and a poor safety profile that requires low basal levels (low ng/mL level) to be maintained over the course of treatment. Temsirolimus on the other hand is a prodrug of sirolimus (rapamycin) and as a result, high levels of rapamycin are

not achieved (< 100 ng/mL) [55]. The administration of ABI-009 led to a much higher exposure to rapamycin (sirolimus) as compared to sirolimus from temsirolimus (C_{max} almost 50 fold higher, AUC almost 12 fold higher for ABI-009) or everolimus (C_{max} 50-70 fold higher, AUC 85-200 fold higher for ABI-009) [38, 55]. Unlike with other mTOR inhibitors, micromolar concentrations are reached and maintained for several hours with ABI-009 which could potentially circumvent acquired resistance to mTOR inhibitors via retroactivation of AKT by TORC2 [56, 57]. The high exposure achieved with ABI-009 with acceptable safety profile could be highly relevant to the treatment of aggressive cancers such as malignant PEComas.

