4.2. Inclusion Criteria

A patient will be eligible for inclusion in this study only if all of the following criteria are met:

1. Patients must have a histologically confirmed diagnosis of malignant PEComa that is either metastatic or locally advanced and for which surgery is not a recommended option.
2. Patients must have available tumor block along with the corresponding pathology report (or approximately 30 unstained slides, with a minimum of 16 slides), and/or fresh biopsy to allow retrospective centralized confirmation of malignant PEComa and for mTOR pathway analysis and biomarker analysis.
3. Patients must have one or more measurable target lesions by CT scan or MRI. Measurable disease by RECIST v1.1.
4. Patients must not have been previously treated with an mTOR inhibitor.
5. Prior treatment (investigational or other), chemotherapy, radiotherapy, surgery, or other therapeutic agents (except mTOR inhibitors) is allowed, if completed after 5 half-lives or ≥ 28 days prior to enrollment, whichever is shorter.
6. Eligible patients, 18 years or older, with Eastern Cooperative Oncology Group (ECOG) performance status 0 or 1.

7. Patients must have the following blood chemistry levels at screening (obtained ≤ 14 days prior to enrollment (local laboratory):
 - a. total bilirubin $\leq 1.5 \times$ upper limit of normal (ULN) mg/dl
 - b. AST $\leq 2.5 \times$ ULN ($\leq 5 \times$ ULN if attributable to liver metastases)
 - c. serum creatinine $\leq 1.5 \times$ ULN
8. Adequate biological parameters as demonstrated by the following blood counts at screening (obtained ≤ 14 days prior to enrollment, local laboratory):
 - a. Absolute neutrophil count (ANC) $\geq 1.5 \times 10^9/L$;
 - b. Platelet count $\geq 100,000/mm^3$ ($100 \times 10^9/L$);
 - c. Hemoglobin ≥ 9 g/dL.
9. Serum triglyceride < 300 mg/dL; serum cholesterol < 350 mg/dL.
10. Male or non-pregnant and non-breast feeding female:
 - Females of child-bearing potential must agree to use effective contraception without interruption from 28 days prior to starting IP and while on study medication and have a negative serum pregnancy test (β -hCG) result at screening and agree to ongoing pregnancy testing during the course of the study, and after the end of study treatment. A second form of birth control is required even if she has had a tubal ligation.

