9.1. Permitted Medications and Procedures

The investigator must be informed as soon as possible about any medication taken from the time of screening until the end of the clinical phase of the study (final study visit). Any concomitant medication(s), including herbal preparations, taken during the study will be recorded in the eCRF. The minimum requirement is that drug name, dose, and the dates of administration are to be recorded. Additionally, a complete list of all prior cancer therapies will be recorded in the eCRF.

Patients should receive full supportive care during the study, including transfusions of blood and blood products, and treatment with antibiotics, anti-emetics, anti-diarrheas, and analgesics, and other care as deemed appropriate, and in accordance with their institutional guidelines. WBC growth factors may be administered at the discretion of the investigator, consistent with institutional guidelines.

Extreme precaution must be taken with contraceptives (either combined or progesterone only), as it is not known if there is the potential of inhibition/induction of enzymes that affect the metabolism of estrogens and/or progestins.

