9.2. Prohibited Medications and Procedures

The use of certain medications, and illicit drugs within 5 half-lives or 28 days, whichever is shorter prior to the first dose of study drug and for the duration of the study will not be allowed. If a prohibited medication is required for single use (such as for a procedure) while study drug is held, the AADi medical monitor can approve such use.

The following medications or non-drug therapies are prohibited:

- Other anti-cancer therapy while on treatment in this study.
- Antiretroviral drugs (patients with known HIV are ineligible for study participation).
- Herbal remedies (eg, St. John's wort) unless approval is granted by the medical monitor.
- Rapamycin is metabolized primarily by CYP3A4. Drugs that are strong inhibitors or inducers of CYP3A4 may only be used under special circumstances (eg, as a single use for a procedure) while treatment with study drug is interrupted. The list may be modified based on emerging data.

- Use of any known CYP3A4 substrates with narrow therapeutic window (such as fentanyl, alfentanil, astemizole, cisapride, dihydroergotamine, pimozide, quinidine, terfanide) within the 14 days prior to receiving the first dose of ABI-009. Other medications may be allowed if there is agreement between the sponsor and investigator
- Use of strong inhibitors and inducers of CYP3A4 within the 14 days prior to receiving the first dose of ABI-009

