All AEs will be recorded by the investigator from the time the patient signs informed consent until 28 days after the last dose of ABI-009 and those SAEs made known to the investigator at any time thereafter that are suspected of being related to IP. AEs and SAEs will be recorded on the AE page of the eCRF and in the patient's source documents. All SAEs must be reported to AADI Drug Safety within 24 hours of the investigator's knowledge of the event by facsimile, or other appropriate method, using the SAE Report Form, or approved equivalent form.

The investigator's clinical judgment is used to determine whether a patient is to be removed from treatment due to an AE. The investigator is responsible for ensuring that all AEs observed by the investigator or reported by the patient that occur after the first

dose of IP through the EOT Visit are reported using the applicable eCRF (eg, Adverse Event Summary CRF).

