11.4. Pregnancy and Breast Feeding Reporting

If a pregnancy occurs in a female patient, or female partner of a male patient, while the patient is taking protocol-required therapies report the pregnancy to AADI as specified below. In addition to reporting any pregnancies occurring during the study, investigators should monitor for pregnancies that occur up to 3 months after the last dose of protocol-required therapies.

The investigator will follow the female patient until completion of the pregnancy, and must notify AADI Drug Safety immediately about the outcome of the pregnancy (either normal or abnormal outcome) using the Pregnancy Follow-up Report Form, or approved equivalent form. If a lactation case occurs while the female patient is taking protocol-required therapies, report the lactation case to AADI as specified below. In addition to reporting a lactation case during the study, investigators should monitor for lactation cases that occur up to 1 week after the last dose of protocol-required therapies.

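### Criterion 10 sets no contraception period for women after the last dose, although the half-life is about 60 h and Section 11.4 monitors for pregnancy to 3 months

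*Combined protocol and SAP*

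**What the plan says.** The Synopsis and Section 4.2 carry the same criterion 10: women of child-bearing potential "must agree to use effective contraception without interruption from 28 days prior to starting IP and while on study medication". The criterion also requires a negative serum test at screening and that the woman "agree to ongoing pregnancy testing during the course of the study, and after the end of study treatment". It therefore mentions the time after treatment for testing, but not for contraception.

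Section 3.3 defines End of Treatment as the date of the last dose. The criterion does not define being on study medication.

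The remaining text on contraceptives, in Section 9.1, is a caution about hormonal products and gives no duration. Table 2 (footnote h) and Section 6.3 require a pregnancy test at the End of Treatment Visit, which detects a pregnancy but does not prevent one.

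Three other sections bear on the time after the last dose:
- Section 1.2.2.3: a high peak "followed by a long half-life of approximately 60 hrs that allows once weekly dosing".
- Section 11.1: adverse events are recorded "until 28 days after the last dose of ABI-009".
- Section 11.4: "investigators should monitor for pregnancies that occur up to 3 months after the last dose".

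**The concern.** The protocol asks for 28 days of contraception before the first dose, when no study drug is present, and for none after the last dose, when drug is present. Adverse event recording, pregnancy testing and pregnancy monitoring all run past the last dose. The contraception duty for women stops with dosing. A woman who ends contraception as soon as treatment ends complies fully with the criterion. If her last dose was recent, she could conceive with drug still in her body, which is the exposure that criterion 10 exists to prevent. This is a question of participant safety and of wording; it does not touch the sample size or any efficacy analysis.

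**Working it through.** The plan states no figure on this point, so there is none to reproduce. The check compares the drug remaining with the time at which the duty ends.

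**Inputs.** Half-life 60 h (Section 1.2.2.3). Doses on Days 1 and 8 of a 21-day cycle (Section 7.1). Yardstick of five half-lives, borrowed from the protocol's washout rule for other drugs in Section 9.2, "within 5 half-lives or 28 days, whichever is shorter prior to the first dose of study drug". Assumption: single-exponential decline from the last dose.

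**Formula.** Fraction left = 0.5^(hours / 60).

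| Time since last dose | Hours / 60 | Fraction left |
|---|---|---|
| 1 day | 24 / 60 = 0.4 | 75.8% |
| 7 days | 168 / 60 = 2.8 | 14.4% |
| 12.5 days | 300 / 60 = 5 | 3.1% |
| 14 days | 336 / 60 = 5.6 | 2.1% |
| 28 days | 672 / 60 = 11.2 | 0.04% |

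Five half-lives = 5 × 60 h = 300 h = 12.5 days. For an assumed half-life range of 48 to 72 h this becomes 10 to 15 days.

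**When the duty ends.** A woman usually learns that a dose was her last only when stopping is decided. The practical question is how long after the dose that decision falls. Time still to run to 12.5 days:
- decision the day after a dose: 12.5 − 1 = 11.5 days;
- decision at the Day 8 visit before dosing, 7 days after the Day 1 dose: 12.5 − 7 = 5.5 days;
- decision at the next Day 1, 14 days after a Day 8 dose: 12.5 − 14 < 0, so none.

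**Which stops come early.** The protocol foresees several: Grade 3 or higher pneumonitis removes the patient permanently (Table 5), a scan for suspected progression may be done at any time (Section 6.2.3), treatment may end by patient or physician choice (Synopsis, Study Treatments; Section 12.1), and a stop may be decided at Day 8.

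**Limits of the arithmetic.** If blood levels fall faster at first than the 60 h half-life implies, the share of peak concentration left is smaller than tabulated. The table shows relative amounts only, because the documents give no concentration below which exposure would be harmless.

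**The case against.** The strongest reply is that most stops fall at or near the 12.5-day yardstick. Scans come every 6 weeks, which is two 3-week cycles, so on schedule they fall near a Day 1, about 14 days after the last Day 8 dose. With the ±3-day window, and if no new dose is given first, that is 11 to 17 days; at 11 days 0.5^(264/60) = 4.7% is left. For general toxicity the drug is held first, and withdrawal is recommended if the event has not settled within 14 days (Section 7.2.1). Grade 2 pneumonitis is held for up to 3 weeks (Table 5). Scheduled chemistry is on Day 1, not Day 8. This stands and confines the gap mainly to the early stops listed above.

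A second reply also stands in part. The half-life supports about 12.5 days, while 3 months (about 90 days) is roughly seven times longer (90 / 12.5 = 7.2). A reader might infer from Section 11.4 that 3 months is the period of fetal risk. The documents do not say so: it is a monitoring window, and monitoring for longer than one requires prevention is not in itself a contradiction. Its merit is that it is the one post-dose pregnancy period the protocol already contains.

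Three further inferences should be resisted:
- **That women receive no instruction.** The consent pages are not in the public file and may state a period. Only the silence of the protocol text can be shown.
- **That pregnancies after the last dose will be missed.** There is a urine test at the End of Treatment Visit, more testing as clinically indicated, and a direction to monitor for 3 months. The lack of a fixed date for later checks does not show that these will fail.
- **That a given share of the 30 patients is exposed.** The female predominance and median age of about 43 in Section 1.1 could at most suggest how many women are of child-bearing potential. They say nothing about how many stop soon after a dose and then drop contraception within days.

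**Conclusion.** The point holds as a gap in a stated rule. Both copies of criterion 10 tie women's contraception to being on study medication, and no section extends it. Followed exactly, the rule allows contraception to lapse with about 14% of drug left at day 7 and 3% at 12.5 days. It matters mainly for women who stop soon after a dose; for a stop decided at the next Day 1 after a Day 8 dose, about 2% remains and the gap is slight.

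The size rests on the stated half-life of about 60 h and on single-exponential decline. Five half-lives is a yardstick taken from another rule in the protocol, not a demonstrated safety limit. The number of women affected cannot be estimated from the documents. The amendment is still worth making, because it is small and serves the purpose the criterion already has.

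**What to change.** In both copies of criterion 10 (Synopsis and Section 4.2), replace *while on study medication* in the women's clause with *while on study medication and for 3 months after the last dose*. This matches the window in Section 11.4. The sponsor's safety team may confirm the length, but it should not be shorter than the 12.5-day washout.

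The cost is one clause in two places, consent wording checked to match, and a longer contraception commitment for women after treatment. No efficacy analysis changes. The end date of the men's duty is a separate matter, and neither it nor an additional follow-up telephone question is needed for this fix.
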